**Clinical Investigational Plan**

1.0 Synopsis

	Details
Title:	A Clinical Evaluation of the Diagnostic Utility of MRI scans in patients implanted with St. Jude Medical pacemakers, ICDs, or CRTs.
Acronym:	SJM MRI Diagnostic Imaging Registry
Purpose:	Assess the diagnostic utility of MRI scans in patients who are implanted with a St. Jude Medical (SJM) pacemaker, ICD, or CRT device.
Objectives:	
Primary Objective
 
Characterize the image quality, clinical impact, and diagnostic utility of MRI in patients undergoing clinically indicated, non-thoracic MRI scans who are implanted with a St. Jude Medical pacemaker, ICD, or CRT device.
Endpoints:	
Primary Endpoint #1:
 
The proportion of MRI scans from pacemakers or CRT-Ps providing sufficient image quality to allow for a diagnostic interpretation. 
Primary Endpoint #2:
 
The proportion of MRI scans from ICDs or CRT-Ds providing sufficient image quality to allow for a diagnostic interpretation.
Design:	
This study is a prospective, non-randomized, multi-center study of subjects implanted with an SJM pacemaker, ICD, or CRT device and who are clinically indicated for a non-thoracic MRI scan.
 
A prospective, multi-center study design was chosen for generalizability of clinical results by enrolling subjects across multiple geographies and sites.
 
The total duration of the study is expected to be 2 to 3 years depending on the rate of enrollment.
 
The study will be conducted in up to 100 centers in the United States.
 
Up to 300 subjects will be enrolled in this study from 2 main device groups (150 subjects with a pacemaker/CRT-P and 150 subjects with an ICD/CRT-D).
 
For each of the 2 main device groups, a minimum of 25 head scans, 25 extremity scans, and 25 lumbar scans will be collected with the remainder of scans to be from any of these 3 scan regions.

Devices used:	This study includes any of the following market released St. Jude Medical pacemaker, ICD, or CRT current generation devices* and any market-released pacing or

**Clinical Investigational Plan**

Details	
	
defibrillation lead:
 
• Pacemakers: Assurity™, Assurity MRI™, Endurity™ and Endurity MRI™• ICDs: Ellipse™ and Fortify Assura™• CRTs: Allure™/Allure Quadra™/Allure Quadra MPT™ CRT-P and Quadra Assura™/Quadra Assura MPT™ CRT-D 
NOTE: *These devices may be part of a system that is FDA approved for MRI scanning.

Study Population	
All patients who meet the inclusion/exclusion criteria, sign an IRB approved informed consent form, and have their device programmed to enter the MRI environment will be considered enrolled as a subject in this study.
 
The study population includes males and females implanted with a St. Jude Medical pacemaker, ICD, or CRT device system and who are clinically indicated for a non-thoracic MRI scan. Vulnerable subjects, such as minors or those unable to provide consent, are excluded from participating.

Inclusion/Exclusion Criteria	
Inclusion Criteria
 
Eligible patients will meet all of the following:
 
• Patient is implanted with a market-released St. Jude Medical pacemaker, ICD, or CRT current generation device listed in the study protocol and any market-released pacing or defibrillation lead.• Patient's device and all leads must be implanted for at least 6 weeks prior to the scheduled date of the MRI.• Patient has a clinical indication for a non-thoracic MRI scan, where MRI is the imaging modality of choice that will give adequate results to manage the patient.• Patient is scheduled for a non-thoracic MRI scan up to 1.5T.• Patient has a pacemaker, ICD, or CRT device implanted pectorally.• Patient has the ability to provide informed consent for study participation and be willing and able to comply with the study procedures.• Patient is 18 years or above, or of legal age to give informed consent specific to state and national law. 
Exclusion Criteria
 
Patients will be excluded if they meet any of the following:
 
• Patient has an ICD/CRT-D and is pacemaker dependent• Capture threshold is greater than 2.5 volts at 0.5 ms for RA and RV leads.

**Clinical Investigational Plan**

Details	
	
• Pacing lead impedance is NOT within normal range (i.e. ≥ 200 and ≤ 2000 ohms)• High voltage lead impedance (HVLI) is NOT within normal range (i.e. ≥ 20 and ≤ 200 ohms)• Patient has a device generator battery voltage at elective replacement interval (ERI)• Patient has another existing active implanted medical device (e.g. neurostimulator, infusion pump, etc.) that has MR labeling that will not allow the MRI scans to be completed.• Patient has other non-MRI compatible device or material implanted 
NOTE:
 
• MRI compatible knee replacements, hip replacements, stents, etc. may be included as long as the labeling of these devices allow for the clinically indicated MRI scans• MRI compatible mechanical, prosthetic, and bioprosthetic heart valves may be included as long as the labeling of these devices allow for the clinically indicated MRI scans• Non-removable dental implants may be included• Patient has a lead extender, adaptor, or capped/abandoned lead• Patient is pregnant
Data Collection	
MRI Scan Visit:
 
Pre-MRI Scan
 
• Obtain informed consent & verify subject eligibility• Obtain medical and surgical history• Obtain demographic information• Obtain implanted SJM pacemaker, ICD, or CRT device system information• Determine the subject's underlying rhythm• Obtain in-clinic device measurements: remaining battery capacity, capture threshold, sense, pacing and HVLI impedances, as applicable 
During MRI Scan
 
• Monitor subject with ECG along with the site's routine monitoring. In cases where ECG monitoring is not readily available, monitoring via pulse oximetry alone is considered acceptable• Assess subject for adverse events

Clinical Investigational Plan

	Details
	
Post MRI Scan (Same day as MRI Scan)
 
• Obtain in-clinic device measurements: remaining battery capacity, capture threshold, sense, pacing and HVLI impedances• Determine the subject's underlying rhythm• Evaluate subject for Adverse Device Effect (ADE), Serious Adverse Device Effect (SADE), Unanticipated Adverse Device Effect (UADE) events and submit an AE CRF (as applicable)• Obtain MRI scan information and clinical evaluation of MRI images• Report deviations, death, and withdrawal, as applicable 
Post MRI Follow-up Visit (Scheduled Visit: 7 days and/or 1-month-Refer to flow chart below)
 
• Obtain in-clinic device measurements: remaining battery capacity, capture threshold, sense, pacing and HVLI impedances• Evaluate subject for Adverse Device Effect (ADE), Serious Adverse Device Effect (SADE), Unanticipated Adverse Device Effect (UADE) events and submit an AE CRF (as applicable)• Report deviations, death, and withdrawal, as applicable 
Unscheduled Visit (if applicable)
 
• Obtain in-clinic device measurements: remaining battery capacity, capture threshold, sense, pacing and HVLI impedances• Evaluate subject for Adverse Device Effect (ADE), Serious Adverse Device Effect (SADE), Unanticipated Adverse Device Effect (UADE) events and submit an AE CRF (as applicable)• Report deviations, death, and withdrawal, as applicable

1.1 Study Flow Chart

Study Flow charts can be found in Section 6.1.

2.0 Background and Justification for Study

Magnetic resonance is the modality of choice for the diagnosis of many musculoskeletal, central nervous system, and cardiovascular diseases.^{1, 2} MRI does not use radiation, has few side effects and is very useful to view soft tissue. In 2007, an estimated 27.5 million MRI procedures were performed in the U.S. in 7,195 hospital and non-hospital sites.³

According to the 2005 World Survey of cardiac pacing and cardioverter defibrillators, 223,425 new pacemakers were implanted in the United States in 2005. When compared to a similar survey conducted in 2001, the 2005 survey showed an increase in the number of pacemakers and defibrillators implanted throughout the world, a trend that is likely to continue into the future.^{4,5} It is estimated that 50-75% of patients with implantable cardiac devices will develop an indication for an MRI scan during the lifetime of their device.⁶

Over the past 10 years, there have been numerous patients with implanted devices who successfully underwent magnetic resonance imaging.^{7,8,9,10,11}

In this prospective, non-randomized, multi-center study, St. Jude Medical plans to develop a registry of patients with SJM pacemakers, ICDs and CRTs who undergo a clinically indicated, non-thoracic MRI scan in order to characterize the image quality, clinical impact, and diagnostic utility of these MRI scans. Adverse events and changes in device measurements related to the MRI scan will also be reported. This study design was chosen to generalize the study results by enrolling subjects across multiple geographies and sites.

3.0 Risks and Benefits of the Clinical Study, including Analysis of Risks

Since subjects enrolling in this study will have an MRI scan performed based on clinical indication at the discretion of the ordering physician, participation in this study will not add additional risk to the subject. The information gathered in this study will add to the understanding of the clinical utility of MRI scans in patients implanted with a pacemaker, ICD, or CRT device system.

3.1 Description of subject population

This study intends to enroll subjects implanted with St. Jude Medical market-released pacemakers, ICDs, and CRTs with a clinical indication for a non-thoracic MRI scan. This population includes males and females 18 years of age or older.

3.2 Anticipated clinical benefits

There are no direct clinical benefits to the subject as a result of their participation in this study since the decision to have an MRI is based on a clinical indication and not a result of this study. All subjects may be more closely monitored by their physician.

Clinical Investigational Plan

3.3 Anticipated adverse events and adverse device effects

Risks associated with the use of SJM market-released pacemaker, ICD, and CRT device systems are anticipated to be comparable to those associated with the use of other market-released pacemaker, ICD, and CRT device systems. Subjects participating in this study have already been implanted with a pacemaker, ICD, or CRT device system as part of their standard medical management and are exposed to, but not limited to, the risk of experiencing the events listed below that are associated with these devices independent of the subject's participation in the study.

While the SJM pacemaker, ICD, and CRT device systems in this study are all market-released, these device systems are not FDA-approved for MRI scans (the device may be part of a system that was FDA approved for MRI scan). Therefore subjects undergoing clinically-indicated MRI scans at the discretion of the ordering physician are therefore exposed to, but not limited to, risk of experiencing the events listed below.

Table 1: Anticipated Events and Anticipated Adverse Device Effects

Event	Mitigation
Potential MRI Related Events 
• Lead electrode heating and tissue damage resulting in loss of sensing or capture or both• Lead heating resulting in thrombus formation or embolism• Device heating resulting in tissue damage in the implant pocket or subject discomfort or both• Induced currents on leads resulting in continuous capture, VT/VF, hemodynamic collapse, or all three• Damage to the device or leads causing:
a. the system to fail to detect or treat irregular heartbeatsb. the system to treat the subject's condition incorrectly• Damage to the functionality or mechanical integrity of the device resulting in the inability of the device to communicate with the programmer	
These risks are mitigated through the selection of investigators who are qualified by training and/or experience to evaluate and treat subjects implanted with a pacemaker, ICD, or CRT device system.
 
In addition, study investigators will be trained on the study protocol to ensure the proper procedures are followed to assure subject safety during the MRI scan. This includes continuous monitoring of the subject using ECG along with the site's routine monitoring. In cases where ECG monitoring is not readily available, monitoring via pulse oximetry alone is considered acceptable during the scan.
 
Advanced Cardiac Life Support (ACLS) procedures will be in place to address situations where a life threatening arrhythmia and/or hemodynamic collapse occurs. The programmer will be used outside the American

**Clinical Investigational Plan**

Event	Mitigation

• Movement or vibration of the device or leads• Lead dislodgment• Competitive pacing and potential for VT/VF induction due to ambulatory asynchronous pacing in MRI mode• Pulmonary Embolism• Death due to untreated spontaneous arrhythmia because tachyarrhythmia therapy is disabled when programmed for the MRI environment	College of Radiology (ACR) defined Zone 4 magnet room. If the subject's hemodynamic function is compromised during the MRI scan, the MRI scan will be stopped, and proper measures will be taken to restore the subject's hemodynamic function.
Potential Pacemaker, ICD, or CRT Device Related Events	

• Refer to the SJM pacemaker, ICD, or CRT user's manual for a full list of potential adverse events	The SJM pacemaker, ICD, or CRT devices in this study are market-released. The adverse events associated with these devices are the same as those associated with other market-released similar devices. These risks are mitigated through the selection of investigators who are qualified by training and/or experience to evaluate and treat subjects implanted with pacemaker, ICD, and CRT device systems.
Potential Lead Related Events	

• Refer to the SJM lead user's manual for a full list of potential adverse events	The SJM pacing and defibrillation leads in this study are market-released. The adverse events associated with these leads are the same as those associated with other market-released similar leads. These risks are mitigated through the selection of investigators who are qualified by training and/or experience to evaluate and treat subjects implanted with pacemaker, ICD, and CRT device systems.

In addition, subjects may also experience unavoidable events related to the MRI scan. An unavoidable event is an event related to the MRI scan that is expected to occur for a

Clinical Investigational Plan

projected duration in all subjects. Unavoidable events are not reportable unless the condition worsens or continues beyond the time frame listed below. Unavoidable events do not need to be reported on an adverse event form if they are resolved within the time frame specified. These events are expected to occur with any MRI scan.

Table 2: Unavoidable events related to the MRI Scan

Event	Time Frame post – MRI scan
• Claustrophobia	• During MRI scan
• Mild diaphoresis	• During and < 1 hour post MRI scan
• Sensation of bodily warmth	• During and < 1 hour post MRI scan
• Sensation of warmth at device pocket not arising to the level of discomfort	• During and < 1 hour post MRI scan
• Hearing impairment	• < 24 hours
• Body stiffness related to immobility	• < 48 hours

3.4 Residual risks associated with the device under investigation

While steps have been taken to identify risks associated with these devices undergoing an MRI scan (Refer to Table 1), there may be risks that are unknown at this time.

3.5 Risks associated with participation in the clinical study

Potential risks associated with the MRI scan are the same as or comparable to those associated with MRI scans of an implanted medical device powered by a battery or other electrical source of power including, but not limited to, those listed in the Adverse Events and Adverse Device Effects section of the protocol.

3.6 Possible interactions with concomitant medical treatments and/or concurrent medical interventions

Since subjects are clinically indicated for an MRI scan, there are no treatments that the subject would not otherwise receive as part of the subject's medical management related to having an implanted pacemaker, ICD, or CRT device system.

The MRI scanner, methods used to scan the subject (scan sequences), and monitoring procedures in and of themselves are not investigational. As such, there are no anticipated interactions with concomitant medical treatments or concurrent medical interventions associated with the MRI scan.

The device checks in this study involve testing of the device and lead that are normally done at a routine device check. As such, there are no anticipated interactions with concomitant medical treatments or concurrent medical interventions associated with this study.

Clinical Investigational Plan

3.7 Steps that will be taken to control or mitigate the risks

The risks associated with MRI scanning of subjects implanted with implantable active medical devices have been identified through clinical evaluation, including an exhaustive literature search.

Risks normally associated with pacemakers, ICDs, CRTs, and transvenous leads will be minimized in the study by selecting investigators who are experienced in treating subjects implanted with these devices and are trained in the this study protocol. Subjects will be actively monitored during the MRI scan using an ECG along with the site's routine monitoring. In cases where ECG monitoring is not readily available, monitoring via pulse oximetry alone is considered acceptable. The investigator and/or other ACLS-certified personnel will be present during the MRI scan to address cases of asystole or hemodynamic collapse that may occur during the MRI scan.

Risks will also be minimized by careful assessment of each subject prior to enrollment. After enrollment, subjects in the study will be assessed as specified in this CIP to monitor the condition of the implanted system after the subject has undergone the MRI scan.

In order to limit the risk of the MRI scan for a subject with an implanted pacemaker, ICD, or CRT device system, the MRI scans will be limited to non-thoracic examinations at up to 1.5T. In addition, the following precautions will be taken based on the AHA Guidelines on Safety of Magnetic Resonance Imaging in Patients with Cardiovascular Devices¹²:

- Advanced cardiovascular life support (ACLS) trained personnel and a “crash cart”, including defibrillator, will be available throughout the procedure to address an adverse event.
- Pre-MRI scan steps outside the MR environment
- Pre-test cardiac device functions
- For pacemaker dependent subjects, reprogram to asynchronous mode
- For ICD/CRT-D, disable bradycardia and tachycardia therapy and detection and exclude pacemaker dependent patients
- The patient’s heart rhythm and vital signs should be monitored throughout the MR procedure.
- Maintain visual and voice contact with the patient throughout the procedure.
- Instruct the patient to alert the MR system operator to any unusual sensations or problems.

After the MRI scan the pacemaker, ICD, or CRT device will be interrogated to verify appropriate device function, to evaluate pacing and sensing characteristics, and to assess any adverse events.

Clinical Investigational Plan

Overall, the clinical study design, subject selection process, and procedures developed for monitoring of the subject during the MRI scan have all been designed to minimize risks to the subject.

While steps have been taken to identify and reduce or minimize risks associated with the MRI scan and participation in the study, there may be risks that are unknown at this time.

3.8 Risk-to-benefit rationale

There may be no direct clinical benefit to the subject for participating in this study; no direct therapy is being provided as part of the study. However, the information gathered in this study will add to the understanding of the clinical utility of MRI scans in patients implanted with a pacemaker, ICD, or CRT device system.

4.0 Study Design

4.1 Purpose

The purpose of this study is to assess the clinical utility of MRI scans in patients who are implanted with a St. Jude Medical pacemaker, ICD, or CRT device. The patient population under study includes male and female patients 18 years or older that are clinically indicated for a non-thoracic MRI scan.

4.2 Study Design and Scope

This study will be performed as part of a regulated, prospective, non-randomized, multi-center clinical study. This multi-center study design was chosen for generalizability of study results by enrolling subjects across multiple geographies and varying types of sites.

The total duration of this study is expected to be 2 to 3 years dependent on the rate of enrollment. The study will be conducted in up to 100 centers in the United States.

Subjects will be enrolled, undergo a clinically-indicated MRI scan, and have an assessment of adverse events, device measurements, and clinical utility of the MRI scan images.

4.2.1 Number of Subjects Required to be Included in the Study

The maximum number of subjects in the study is 300 from 2 main device groups (150 subjects with a pacemaker/CRT-P and 150 subjects with an ICD/CRT-D. A maximum of 45 subject enrollments will be allowed per center (15% of total subjects enrolled). For each of the 2 main device groups, a minimum of 25 head scans, 25 extremity scans, and 25 lumbar scans will be collected with the remainder of scans to be from any of these 3 scan regions.

Clinical Investigational Plan

A patient will be considered enrolled in the study after he/she meets the inclusion/exclusion criteria, signs an IRB-approved informed consent form, and the subject's device is programmed to enter the MRI environment.

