4.6 Subject Population

4.6.1 Patient Screening

All patients presenting at the investigational site may be screened by a member of the investigational team who has been trained on the CIP and delegated to do so.

Patients who do not meet the inclusion/exclusion criteria will not be eligible to participate in this study.

Patients meeting the inclusion/exclusion criteria will be fully informed about the study and asked to review and sign informed consent. If the subject agrees, a duly signed and dated Patient Informed Consent will be obtained.

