6.5.3 Clinical Evaluation of MRI Scan

The radiologist will review the clinically-indicated MRI scan for diagnostic interpretation. The following information will be collected regarding the MRI scan, and are not limited to:

- Primary reason for MRI scan
- Body region scanned (non-thoracic) (e.g. brain, cervical spine, lumbar spine, knee, shoulder, hip, hand/wrist)
- MRI System used (i.e. brand, model, software version, etc.)
- Duration of scan (min)
- Whole body SAR
- Image quality (i.e. sufficient or insufficient to interpret the MRI image)
- Clinical Diagnosis (e.g. joint abnormality, vascular abnormality, no abnormalities, etc.)

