12.1 Statistical design, hypotheses, method and analytical procedures

12.1.1 Primary endpoint#1:

The proportion of MRI scans from pacemakers or CRT-Ps providing sufficient quality to allow for a diagnostic interpretation.

The primary endpoint will be reported as the number of MRI scans providing sufficient quality to allow for a diagnostic interpretation divided by total number of MRI scans along with the 95% lower confidence bound (LCB) calculated using Clopper-Pearson exact method.

12.1.2 Primary endpoint#2:

The proportion of MRI scans from ICDs or CRT-Ds providing sufficient quality to allow for a diagnostic interpretation.

The primary endpoint will be reported as the number of MRI scans providing sufficient quality to allow for a diagnostic interpretation divided by total number of MRI scans along with the 95% lower confidence bound (LCB) calculated using Clopper-Pearson exact method.

Clinical Investigational Plan

12.1.3 Additional Data:

- Demographics: gender, age, ethnicity, race, cardiac disease history, arrhythmia history, etc.
- A summary of scan location (i.e. head, extremity, lumbar)
- A summary of clinical findings based on review of MRI scans
- A summary of device electrical measurements at the MRI Scan Visit (before and immediately after the MRI scan) and at subsequent Follow-up Visit(s).
- A summary of adverse events (ADE, SADE, UADE)
- A summary of MRI-related complications
- Mortality
- Estimate of the incidence rate of device patients undergoing a clinically indicated MRI scan.

The above data will be summarized by each main device group (pacemaker/CRT-P and ICD/CRT-D).

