12.2 Sample size

Assuming 95% of the MRI scans are of sufficient quality to allow for a diagnostic interpretation, a sample size of 150 MRI scans for each of the two main device groups (Pacemaker/CRT-P and ICD/CRT-D) provides a 95% confidence interval half-width of 4.0%.

For each of the 2 main device groups, a minimum of 25 head scans, 25 extremity scans, and 25 lumbar scans will be collected, with the remainder of scans to be from any of these 3 scan regions in order to ensure an adequate distribution of these different scan regions.

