12.8 The treatment of missing, unused or spurious data, including drop-outs and withdrawals

There are no plans to perform imputations for missing data, subject dropouts or withdrawals. If spurious data are discovered, these data will be excluded from analyses. Reasons for exclusion of any data from analyses will be summarized.

12.9 The exclusion of particular information for the testing of the hypothesis, if relevant

There is no hypothesis for this study.

12.10 In multi-center studies, the minimum and maximum number of subjects to be included for each center

A minimum of 1 subject and a maximum of 45 subjects may be included at each center enrolling in the study.

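### Does the cap of 45 subjects per center let one center dominate a primary endpoint that rests on only 150 scans?

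*Combined protocol and SAP*

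**What the plan says.** The cap appears twice in the Clinical Investigational Plan, and the two places agree. Section 4.2.1: "A maximum of 45 subject enrollments will be allowed per center (15% of total subjects enrolled"). Section 12.10: "A minimum of 1 subject and a maximum of 45 subjects may be included at each center enrolling in the study". Both count enrollments over the two device groups together.

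The primary endpoints are not pooled over the groups. Section 12.2 plans "a sample size of 150 MRI scans for each of the two main device groups", and section 12.1 reports each group's proportion "along with the 95% lower confidence bound (LCB) calculated using Clopper-Pearson exact method". Section 12.6 plans no subgroup analyses. Nothing in section 12 describes a by-center table, a leave-one-center-out estimate or an allowance for clustering.

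Other passages bear on how likely concentration is and what it could affect:

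- Section 4.2, purpose: "This multi-center study design was chosen for generalizability of study results by enrolling subjects across multiple geographies and varying types of sites".
- Section 4.2, size: "The study will be conducted in up to 100 centers in the United States".
- Section 4.6.1: "All patients presenting at the investigational site may be screened by a member of the investigational team".
- Section 6.5.3: "The radiologist will review the clinically-indicated MRI scan for diagnostic interpretation". Sufficiency of image quality is recorded as a yes/no judgment, and no central read is described.
- Sections 12.3 and 12.9: no pass/fail criterion and no hypothesis.

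**The concern.** The cap is the only stated limit on how far one center can dominate, and it is scaled to a total of 300 on which no primary endpoint is estimated. The revision history (Appendix B) shows that version D doubled enrollment, split the endpoint by device group, and raised the cap from 22 to 45 to hold it at 15% of the total. A 15% limit on the whole study therefore allows up to 30% of one endpoint.

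Two things would be at stake. One is generalizability, the stated reason for using many centers: an estimate that leans on one center's scanner and radiologists says less about other sites. The other is precision: the Clopper-Pearson bound treats scans as independent, and a large center with its own image-quality rate would make that bound somewhat too tight. A reader of the planned output could see neither.

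**Working it through.** **Inputs from the plan.** Cap 45 (4.2.1, 12.10); total 300 and 150 per group (4.2.1); assumed sufficiency 95% and half-width 4.0% (12.2); up to 100 centers (4.2). The plan gives no intraclass correlation (ICC), so 0.01, 0.02 and 0.05 are assumptions. The 95% lower bound is taken as one-sided.

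**The plan's own figures.**
- Cap: 45/300 = 15%, as stated.
- Precision: the two-sided Clopper-Pearson interval at 142/150 is 89.76% to 97.67%, half-width 3.95%, which rounds to 4.0%. The one-sided bound at 95% of 150 lies 4.00 points below 95%.

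**Share of one endpoint.** Worst case 45/150 = 30%. A center at the cap with an even device split supplies about 15% of each endpoint. If all 100 centers take part, the average is 300/100 = 3 subjects per center.

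**Effect on precision.** Design effect DE = 1 + (Σm²/Σm − 1) × ICC, with m the scans per center. The bound is recomputed at an effective sample size of 150/DE.

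| Layout of 150 scans | Σm²/Σm | DE at ICC 0.01 / 0.02 / 0.05 | Points below 95% |
|---|---|---|---|
| One center of 45, 35 of 3 | 15.6 | 1.15 / 1.29 / 1.73 | 4.4 / 4.7 / 5.8 |
| One of 22, 42 of 3, one of 2 | 5.77 | 1.05 / 1.10 / 1.24 | 4.1 / 4.3 / 4.6 |
| 50 centers of 3 | 3.0 | 1.02 / 1.04 / 1.10 | 4.1 / 4.1 / 4.3 |
| Independent scans | – | 1 | 4.0 |

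**Effect on the estimate.** Between-center SD = √(ICC × 0.95 × 0.05) = 2.18 / 3.08 / 4.87 points. Shift = share × difference from the other centers.
- 30% share, 1 SD: 0.65 / 0.92 / 1.46 points.
- 30% share, 2 SD: 1.31 / 1.85 / 2.92 points.
- 15% share, 1 SD: 0.33 / 0.46 / 0.73 points.

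All lie below the planned 4.0. To exceed it, the 45-scan center would need a rate near 80% against 95% elsewhere: 0.30 × 15 = 4.5 points.

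**What leaving out the largest center would reveal.** At 95% sufficiency a 45-scan center is expected to have 0.05 × 45 = 2.25 insufficient scans. Take 41/45 there and 101/105 elsewhere.
- All scans: 142/150 = 94.7%, lower bound 90.6%.
- Without that center: 101/105 = 96.2%, lower bound 91.5%.

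This looks like a center effect but is compatible with chance. Fisher's exact test gives p = 0.24. With a true rate of 95% everywhere, P(at least 4 insufficient of 45) is about 19%. Under the same no-effect assumption, dropping 45 of 150 scans moves the estimate by 1.5 points or more in about 20% of trials. The bound also widens: at 95% it lies about 5.1 points below with 105 scans, against 4.0 with 150.

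**What a per-group limit would do.** 15% of 150 is 22.5, so 22 per center per group. Each subject belongs to one group, so a center could then enroll at most 22 + 22 = 44, and the overall limit of 45 could never be reached. Filling a group would take at least ⌈150/22⌉ = 7 centers instead of ⌈150/45⌉ = 4.

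**The case for a change.** The strongest case for a change is that a descriptive study has nothing but its estimates. Generalizability is its stated aim, and image quality may well vary with scanner and reader. Showing the largest center's share, and the result without it, needs no new data, and fixing it in advance avoids a later selective choice. Nor is 30% the extreme of what the cap permits. Three centers of 45 and one of 15 could fill a group, giving Σm²/Σm = 6300/150 = 42 and DE = 1.41 / 1.82 / 3.05. The share also rises if a group ends short of 150 completed scans: with an assumed 120 it would be 45/120 = 37.5%.

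The facts in this stand: no rule limits a center's share within a group, and no by-center look is planned. The inference that the plan must change does not. Concentration of that kind is permitted, but nothing in the documents makes it likely: up to 100 centers may take part, screening is open to all patients presenting, and the eligible devices cover both groups. The proposed check also misses half the complaint. A Clopper-Pearson bound recomputed without one center still assumes independent scans, so clustering would remain unaddressed. A per-group limit would spread enrollment, but centers that see mainly one device type would stop sooner and recruitment could slow. That is a trade-off the sponsor may reasonably settle either way.

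**Conclusion.** The observation is accurate, but it is not an error and needs no amendment. The cap is 15% of the total, as stated, and the plan promises nothing about shares within a device group.

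The size is modest. With one center at 30%, the rest at 3 scans each and an ICC of 0.01 to 0.02, the lower bound falls 0.4 to 0.7 points further below 95% than under independence; at 0.05 it falls about 1.7 to 1.8 points further. A 1 SD center moves the estimate by 0.7 to 1.5 points, within the planned 4.0. These figures rest on assumed ICCs and an assumed layout of centers. Heavier concentration or a center rate near 80% would do more.

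No decision depends on the result, since there is no hypothesis and no pass/fail criterion. The sensitivity analysis would leave the primary estimate and bound unchanged and would often show a 1 to 2 point difference by chance alone. The remaining gap is one analysts can fill sensibly at reporting: state the number and share of scans from the largest center for each endpoint, with the estimate excluding it if wanted, read as description only.
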